15.1 Adverse Events

All AEs recorded during the course of the study will be coded with the MedDRA, latest version at time of data base lock, and assigned to a SOC and a PT.

Treatment-emergent AEs (TEAEs) are those events with onset dates on or after the first administration of study intervention on Day 1. Any AE occurring before the administration of study intervention on Day 1 and resolved before administration of study intervention or not worsening after administration of study intervention in intervention on Day 1 will be included in the AE listings but will not be included in the summary tables (unless otherwise stated). These will be referred to as “pre-treatment” AEs. An AE occurring after administration of any study intervention will be counted towards the last intervention received before the onset, even if the event is not resolved at the beginning of the following intervention. An AE that worsens after a later intervention period will be counted towards both study interventions.

In case AE-related dates are partial, the available information will be used in a conservative approach to determine whether the AE is treatment-emergent.

All analyses described in Section 15.1 will be based on TEAEs if not otherwise specified. The AE listings will include all AEs (whether treatment-emergent or not). AEs outside the on-treatment period will be flagged in the listings.

Unless otherwise specified, TEAEs will be summarized, by number and percentage of participants with the TEAE in the category of interest, as well as the number of events, in total and by study intervention group, primary SOC and PT in alphabetical order for SOC and decreasing overall frequency for PT.

Each participant will be counted only once within each SOC or PT.

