8.3 Adverse Events, Serious Adverse Events, and Other Safety Reporting

- The definitions of an AE and a SAE are in [Appendix 4](#).
- The Investigator and any qualified designees (e.g., Sub-Investigators) are responsible for detecting, documenting, and recording events that meet the definition of an AE or SAE. The Investigator remains responsible for following up AEs that are serious, considered related to the study intervention or study procedures, or that caused the participant to discontinue the study intervention or study, as specified in Section 8.3.2.
- Requests for follow-up will usually be made via the Sponsor or clinical research organization-designated study team member, although in exceptional circumstances the global patient safety department may contact the Investigator directly to obtain further information or to discuss the event.
- The method of recording, evaluating, and assessing causality of AEs and SAEs and the procedures for completing and transmitting SAE reports are in [Appendix 4](#).
- All AEs and SAEs will be collected from the signing of the ICF until the Safety Follow-up Visit at the time points specified in the Schedule of Assessments (Section 1.3). Beyond this reporting period, any new unsolicited SAEs that the Investigator spontaneously reports to the Sponsor will be collected and processed.
- All SAEs will be recorded and reported to the Sponsor or designee immediately, as indicated in [Appendix 4](#). The Investigator will submit any updated SAE data to the Sponsor within 24 hours of it being available using the same procedure that was used for the initial report.

- Investigators are not obligated to actively solicit information on AEs or SAEs after the end of study participation. However, if the Investigator learns of any SAE, including a death, at any time after a participant has been discharged from the study, and he/she considers the event to be reasonably related to the study intervention or study participation, the Investigator will promptly notify the Sponsor.

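### SAP 15.1 gives two rules for treatment emergence that do not match, so an adverse event that begins before dosing and worsens afterwards has no class and no intervention column

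*SAP*

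**What the plan says.** The nature, occurrence and severity of TEAEs is a secondary endpoint (Protocol section 3, SAP section 5). The protocol does not define the term. The rules are in SAP 15.1:

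- **Definition.** "Treatment-emergent AEs (TEAEs) are those events with onset dates on or after the first administration of study intervention on Day 1".
- **Pre-treatment events.** These begin before the Day 1 administration and are "resolved before administration of study intervention or not worsening after administration of study intervention in intervention on Day 1". They "will be included in the AE listings but will not be included in the summary tables (unless otherwise stated").
- **Attribution.** An event after dosing "will be counted towards the last intervention received before the onset". The paragraph adds: "An AE that worsens after a later intervention period will be counted towards both study interventions".
- **Scope.** "All analyses described in Section 15.1 will be based on TEAEs if not otherwise specified".

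SAP 15.1.2 limits the listing of events leading to discontinuation to TEAEs as well.

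Pre-dose events do enter the database. Protocol 8.3 states: "All AEs and SAEs will be collected from the signing of the ICF until the Safety Follow-up Visit". Screening runs from Day -28.

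**The concern.** A definition of treatment emergence should catch two kinds of event: those that start on treatment, and those already present that get worse on treatment. The SAP's definition covers only the first. The pre-treatment sentence plainly has the second kind in mind, because it makes non-worsening a condition for leaving an event out of the tables. The two sentences therefore divide events along different lines, and nothing says which one governs.

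The Day 1 wording adds a second gap. Day 1 is the cocktail in Part 1 and sumatriptan in Part 2. Evobrutinib, the investigational drug, starts on Day 4 in Part 1 and Day 2 in Part 2 (Protocol 4.2, 5.3.1 and 6.1). If worsening is judged only against the Day 1 administration, an event that first worsens on evobrutinib is still classed as pre-treatment.

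What is at stake is the count behind a secondary endpoint. Two programmers could follow the same SAP and produce different TEAE tables from the same data.

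**Working it through.** The SAP gives no figure to reproduce. The check is to read the two sentences as logical conditions and classify each type of event under both.

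| Event | Definition sentence | Pre-treatment sentence | Agree? |
|---|---|---|---|
| Onset after first dose | TEAE | Not pre-treatment | Yes |
| Onset before first dose, resolved before it | Not a TEAE | Pre-treatment | Yes |
| Onset before first dose, never worsens | Not a TEAE | Pre-treatment | Yes |
| Onset before first dose, worsens after the Day 1 dose | Not a TEAE | Not pre-treatment, so by implication tabulated | **No** |
| Onset before first dose, stable after the Day 1 dose, first worsens on evobrutinib | Not a TEAE | Pre-treatment if the Day 1 words are read literally | Agree, but the worsening is missed |

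**Fourth row.** The event falls in neither class. If the definition governs, the scope sentence removes it from the 15.1 tables, and 15.1.2 removes it from the discontinuation listing. If the pre-treatment sentence governs, it is tabulated, but the SAP does not say in which column: attribution runs to the last intervention before onset, and there was none.

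**Fifth row.** As an illustration, take a mild headache that starts on Day -1 in Part 1, is unchanged after the cocktail and becomes moderate on Day 5. Its onset is too early for the definition. It did not worsen after the Day 1 administration, so it is listed as pre-treatment. The sentence on worsening after a later intervention does not clearly rescue it, because counting towards both interventions presupposes an earlier one.

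**Other rules that might settle it.** The partial-date rule in 15.1 deals with incomplete dates, not worsening. SAP 9.3 allows several records for one event but does not say which record's start date decides treatment emergence.

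**Size.** Each part has at most 20 participants (Protocol synopsis), and SAP section 9 takes AE percentages over those who received the intervention.

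- 1/20 = 5.0%
- 1/16 = 6.25%, if only 16 received it

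SAP 15.1.1 has a table of non-serious TEAEs with a cutoff of 5% in any intervention arm. One participant is enough to reach that cutoff, so one reclassified participant can decide whether a preferred term appears. The documents give no rate of pre-dose events or of worsening, so an expected number cannot be derived from them.

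**The case against.** The strongest reply is that the intent is clear. The pre-treatment sentence excludes only events that resolved or did not worsen, so its natural reading keeps worsening events in the tables. That carries weight. A reader might infer that worsening events are lost from all TEAE tables, and the documents do not support that; it follows only if the definition is applied on its own. But the implication does not repair the definition, to which the 15.1 analyses are tied, and it supplies no attribution.

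A reader might also infer that such events are summarised nowhere. That is wrong too. SAP 15.2.2 tabulates SAEs and 15.2.3 tabulates AESIs, neither with a TEAE limit, and the AE listings contain all events. The exposure is to non-serious events that are not AESIs.

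A worsening might also be recorded as a new event with a post-dose onset. Protocol Appendix 4 treats exacerbation of a pre-existing condition as an AE, and SAP 9.3 foresees several records per event. This route would solve the problem if it were the convention, but neither document says that it is.

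A third tempting reading is that an event on Day 1 before the dose would be counted under the cocktail or sumatriptan because the definition speaks of dates. This does not hold. The definition is anchored to the administration, the pre-treatment sentence covers pre-dose events expressly, and attribution to the last intervention before onset gives such an event no column. The reference to dates is loose and worth tidying, no more.

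Finally, the Day 1 words at the end of the non-worsening condition look like an editing slip, not a deliberate exclusion. That is likely, and is a reason to correct them.

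**Conclusion.** The mismatch is real and lies within one paragraph of the SAP. A pre-dose event that worsens after dosing is neither treatment-emergent nor pre-treatment, and has no intervention column. Applying the stated definition literally gives a wrong count for a secondary endpoint, including for worsening first seen on evobrutinib.

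The practical effect is likely to be small. Participants are healthy, an infection between Screening and admission excludes (Protocol 5.2), and eligibility is rechecked on Day -1. The safety analysis is descriptive, and the primary PK endpoints are untouched. Against that, one participant is 5 percentage points of 20. The conclusion assumes that a worsening is not routinely entered as a new event with its own onset; if it is, the gap closes in practice, but the SAP should say so. It should be corrected because the text is contradictory and the repair is cheap, not because many events are expected to be affected.

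**What to change.** Amend SAP 15.1 as follows:

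1. **Definition.** A TEAE is an AE with onset date and time at or after the first dose of any study intervention, or an AE with earlier onset that worsens in severity after any dose of any study intervention.
2. **Attribution.** Count a worsened AE towards the last intervention received before the worsening. An AE that began under an earlier intervention stays counted there too, as the SAP already provides.
3. **Pre-treatment sentence.** Delete the last five words of "resolved before administration of study intervention or not worsening after administration of study intervention in intervention on Day 1", so that worsening after any later dose, including evobrutinib, is recognised.
4. **Day 1 onsets.** Classify by clock time: at or after the dose is a TEAE, before the dose is pre-treatment unless it later worsens, and a missing time is treated as a TEAE.

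The cost is SAP wording and a small change to the derivation program. SAP 9.3 already uses AE start times, so the clock-time rule needs nothing new. The attribution rule needs a date for the worsening. Protocol Appendix 4 requires an intensity for each AE but does not say that dated changes are captured. Before adopting the rule, confirm that the eCRF records the date of a severity change, or state that a worsening is entered as a new AE record.

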15.1.1 All Adverse Events

Treatment-emergent AEs and participants experiencing TEAEs will be summarized separately for Part 1 (Cocktail, Evobrutinib, Evobrutinib+Cocktail and overall) and Part 2 (Sumatriptan, Evobrutinib, Evobrutinib+Sumatriptan and overall) with::

- The number and percentage of participants with any TEAE, any related TEAE, any cocktail-related TEAE, any evobrutinib-related TEAE, any sumatriptan-related TEAE, any

serious TEAE, any related serious TEAE, any cocktail-related serious TEAE, any evobrutinib related serious TEAE, any sumatriptan-related serious TEAE, any severe TEAE, any related severe TEAE, any cocktail-related severe TEAE, any evobrutinib-related severe TEAE, any sumatriptan-related severe TEAE, any AEs of special interest (AESI), any TEAE leading to death, any related TEAE leading to death, any cocktail-related TEAE leading to death, any evobrutinib-related TEAE leading to death, any sumatriptan-related TEAE leading to death, any TEAE leading to study discontinuation

- The number and percentage of participants with at least one TEAE and the number of events by SOC and PT.
- The number and percentage of participants with TEAEs excluding SAEs and the number of events, with frequency $\geq 5\%$ in any study intervention arm by SOC and PT
- The number and percentage of participants with at least one TEAE and the number of events by severity, SOC, and PT
- The number and percentage of participants with at least one related TEAE, cocktail-related TEAE, evobrutinib-related TEAE, sumatriptan-related TEAE and the number of events by SOC and PT
- The number and percentage of participants with at least one AESI recorded and the number of events by SOC and PT.

Unless otherwise stated, AEs will be displayed with SOC terms sorted alphabetically and PTs within each SOC term sorted in descending overall frequency.

For determining incidence counts, within each level of TEAE term, if a participant experiences more than one occurrence, the participant will only be counted once for that TEAE.

Adverse events related to any study intervention are those events with relationship missing, unknown or yes.

In case a participant had events with missing and non-missing severity, the maximum non-missing severity will be displayed.

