4.1 Overall Design

Study Design	Nonrandomized, open-label, single-sequence (for each part; Sections 1.2 and 1.3)
Control Method	Not applicable
Single or Multicenter	Single center
Control Group	Not applicable
Study Population Type	Healthy participants (Section 5.1)
Level and Method of Blinding	Not applicable
Bias Minimalization Method(s)	Not applicable
Study Intervention Assignment Method	Not applicable
Involvement of Special Committee(s):	No
Total Duration of Study Participation per Participant	Up to 6 weeks, including the Screening period (maximum 4 weeks) and a maximum of 2 weeks of intervention period, including the Safety Follow-up on the day after the last dose of study intervention, Day 13 for Part 1 and Day 9 for Part 2 (Sections 1.2 and 1.3).
Provisions for Study Extension or Entry into Roll-Over Studies	Not applicable
Adaptive Aspects of Study Design	Not applicable

A study scheme and a detailed Schedule of Assessments are provided in Section 1.2 and Section 1.3, respectively.

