8.2 Subgroup Definition and Parameterization

Not applicable.

9 General Specifications for Data Analyses

The results of this study will be reported using summary tables, figures, and data listings, as appropriate. All data will be summarized by study intervention and/or scheduled time point, as applicable.

Listings

In the individual participant data listing all individual data will be listed by part as measured. Repeated and unscheduled measurements will be included in the listings. All listings will be sorted by study intervention, subject ID, and nominal time point, as appropriate.

Tables and Descriptive Statistics

All data will be summarized by study intervention and nominal time point, as appropriate. Repeated and unscheduled measurements included in the listings will not be used for statistical analyses or summaries, unless the repeated measurement was performed due to unreliable values/technical reasons, e.g., clotted samples.

Unless otherwise specified, continuous variables will be summarized using descriptive statistics, i.e. the number of participants with non-missing values (n), the number of participants with missing values, (nmiss), mean, standard deviation, median, 25th percentile (Q1) and 75th percentile (Q3), minimum, and maximum. If there are no missing values the number of participants with missing

values should be indicated by a 0. Mean, Median, Q1, Q3, Min, Max will have the same precision as the SDTM data (decimal places). SD will be presented with one decimal place more than the mean.

Qualitative variables will be summarized by frequency counts and percentages. Unless otherwise stated the calculation of proportions will be based on the number of participants of the analysis set of interest that received the respective study intervention for AE and PK tables and for all other evaluations the analysis set of interest [N]. Therefore, counts of missing observations will be included in the denominator and presented as a separate category.

Study day 1 for this study is defined as the start date of study intervention.

Unless otherwise specified, comparisons will be presented for substrates cocktail with evobrutinib vs. substrates cocktail alone of part 1 and sumatriptan with evobrutinib vs. sumatriptan alone of part 2.

The following labels will be used for the study interventions in tables and listings of Part 1, if not stated otherwise:

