Cocktail (Day 1):	Single oral dose substrate cocktail on Day 1: digoxin (0.25 mg), metformin (10 mg), rosuvastatin (10 mg)
Evobrutinib (Days 4 to 9):	45 mg Evobrutinib multiple doses twice daily on Days 4 to 9
Evobrutinib+Cocktail (Day 10):	45 mg Evobrutinib multiple oral doses twice daily on Days 4 to 12 plus Cocktail on Day 10

The following labels will be used for the study interventions in tables and listings of Part 2, if not stated otherwise:

Sumatriptan (Day 1):	25 mg Sumatriptan single oral dose on Day 1
Evobrutinib (Days 2 to 7):	45 mg Evobrutinib multiple doses twice daily on Days 2 to 7
Evobrutinib+Sumatriptan (Day 8):	45 mg Evobrutinib multiple doses twice daily on Days 2 to 8 plus Sumatriptan on Day 8

Note: The label "Evobrutinib" is applicable to adverse event (AE) tables and listings only.

All tables, listings and figures will be provided by part.

All statistical analyses will be performed using SAS® Software version 9.2 or higher.

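### The evobrutinib-alone column of the AE tables collects events for about 6 days, against about 1 day (Part 2) or 3 days (Part 1) in the columns beside it, with no time at risk shown

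*SAP*

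**What the plan says.** TEAEs are a secondary endpoint (Protocol Section 3), and Protocol 9.4.2 asks for them to be summarised by treatment. SAP 15.1.1 sets the columns: "Treatment-emergent AEs and participants experiencing TEAEs will be summarized separately for Part 1 (Cocktail, Evobrutinib, Evobrutinib+Cocktail and overall) and Part 2", the Part 2 columns being sumatriptan, evobrutinib, the combination and overall.

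SAP 15.1 gives the metric: "by number and percentage of participants with the TEAE in the category of interest, as well as the number of events". SAP Section 9 (General Specifications for Data Analyses) gives the denominator: the "calculation of proportions will be based on the number of participants of the analysis set of interest that received the respective study intervention". That is a count of people, not of time.

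SAP 15.1 also gives the attribution rule. An event "will be counted towards the last intervention received before the onset", so a column stays open until the next intervention begins.

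The treatment labels in SAP Section 9 fix the lengths. In Part 2 the first column is "25 mg Sumatriptan single oral dose on Day 1" and the second is "45 mg Evobrutinib multiple doses twice daily on Days 2 to 7". In Part 1 evobrutinib alone covers Days 4 to 9. Protocol 4.1 closes the last column, "including the Safety Follow-up on the day after the last dose of study intervention, Day 13 for Part 1 and Day 9 for Part 2".

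SAP 9.3 derives AE duration and time from dosing, and SAP 13 lists dosing times. Neither section nor SAP 15 defines time at risk, a rate or a column boundary.

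**The concern.** Columns of one table are read against each other, and SAP 15.1.1 itself speaks of TEAEs "in any study intervention arm by SOC and PT". Evobrutinib alone is a natural reference for asking whether adding a substrate worsens tolerability, and SAP Section 9 creates that column for AE tables and listings only. A column that is open longer gathers more events and more affected participants even when the daily risk is the same. A lower percentage for the combination than for evobrutinib alone could then be taken as reassurance when it reflects a shorter look. A real increase under co-administration could be masked in the same way.

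**Working it through.** **Window lengths.** These are counted from the labels in SAP Section 9 and the follow-up days in Protocol 4.1.

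| | Substrate alone | Evobrutinib alone | Combination | Sum |
|---|---|---|---|---|
| Part 1 | Days 1–3: 3 days | Days 4–9: 6 days | Day 10 to follow-up on Day 13: 3 days | 12 |
| Part 2 | Day 1: 1 day | Days 2–7: 6 days | Day 8 to follow-up on Day 9: 1 day | 8 |

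The sums reproduce the treatment durations in the Protocol synopsis (12 and 8 days). The evobrutinib days, 6 + 3 = 9 and 6 + 1 = 7, reproduce those in Protocol 2.3.

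**Expected percentages with no true difference.** The documents give no daily TEAE rate, so r = 0.02, 0.05 and 0.10 per participant-day are assumptions. With one constant rate in every column, P(at least one TEAE in t days) = 1 − exp(−r·t).

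| r | t = 1 day (Part 2, short columns) | t = 3 days (Part 1, short columns) | t = 6 days (evobrutinib alone) |
|---|---|---|---|
| 0.02 | 2.0% | 5.8% | 11.3% |
| 0.05 | 4.9% | 13.9% | 25.9% |
| 0.10 | 9.5% | 25.9% | 45.1% |

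The ratio of evobrutinib alone to a short column is about 4.7 to 5.7 in Part 2 and 1.7 to 1.9 in Part 1.

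**Event counts.** Under any constant common rate, evobrutinib alone collects 6/8 = 75% of events in Part 2 and 6/12 = 50% in Part 1.

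**Chance of the misleading ordering.** The day-by-day form 1 − (1 − 0.05)^t gives nearly the same percentages: 26.5%, 14.3% and 5.0% for 6, 3 and 1 days. Take 20 participants per part and treat two columns as independent binomials. This is an approximation, since the same people contribute to both. Evobrutinib alone then shows more affected participants than the combination with probability 78% in Part 1 and 96% in Part 2, with equal daily risk.

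**Masking.** Suppose co-administration doubles the rate from 0.05 to 0.10. Part 1 would show 1 − exp(−0.10 × 3) = 25.9% for the combination against 25.9% for evobrutinib alone. Part 2 would show 1 − exp(−0.10 × 1) = 9.5% against 25.9%.

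**Boundary.** Evobrutinib is given again on the evening of Day 10 (Part 1) or Day 8 (Part 2), and on Days 11 and 12 in Part 1. Read literally, the last-intervention rule could send events after those doses to evobrutinib alone. With doses 12 hours apart, the windows would become about 3 / 8.5 / 0.5 days and 1 / 6.5 / 0.5 days. At r = 0.05, evobrutinib alone would show 1 − exp(−0.05 × 8.5) = 34.6% in Part 1 and 1 − exp(−0.05 × 6.5) = 27.7% in Part 2, against 1 − exp(−0.05 × 0.5) = 2.5% for the combination in each. The labels suggest this is not intended, but no text rules it out.

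**Participant-days.** With 20 participants and no dropout, the totals are 60 / 120 / 60 in Part 1 and 20 / 120 / 20 in Part 2.

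**The case against.** The strongest reply is that the comparison the SAP names is sound. Section 9 makes combination against substrate alone the default, and those windows are nominally equal: 3 against 3 days and 1 against 1 day. This stands. A reader might infer that the tables make the combination look safer in general. The documents do not support that: the distortion arises only where evobrutinib alone is one side of the contrast.

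Other parts also stand. Protocol 9.1 makes the analysis descriptive, and no text plans a claim that co-administration adds no harm. The evobrutinib label shows its day range, and the listings would let a careful reader rebuild the windows. The combination labels, however, name only Day 10 or Day 8 and do not show how long those columns stay open. Part 1, at 2:1, is a mild case. The 5% reporting threshold adds nothing to the concern: with at most 20 participants, one person is already 1/20 = 5%.

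The constant rate is a real limit. If events fell only in the first day after each intervention started, the crude percentages would be comparable. Dividing by time would then understate evobrutinib alone, by a factor of 6 relative to the Part 2 short columns and 2 relative to Part 1. Rates are also imprecise: in a Part 2 short column one event moves the rate by 1/20 = 0.05 per day. Nor do they undo the fixed order of treatments. It is therefore tempting, but wrong, to make rates the only basis for comparing columns.

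None of this removes the gap. The table still gives a reader no measure of how long each column was observed.

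**Conclusion.** The point holds for evobrutinib alone against either neighbouring column, mainly in Part 2 (6:1) and mildly in Part 1 (2:1). At an assumed equal rate of 0.05 per participant-day, observation time alone gives about 26% against 5% in Part 2 and about 26% against 14% in Part 1. The window lengths come from the documents. The percentages depend on the assumed rate and on its being roughly constant, and early clustering of events would shrink them.

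Combination against substrate alone is not affected, provided the boundaries are those the labels imply. A reader might infer that it also needs a fixed 72-hour or 24-hour window after the substrate dose. It does not once the boundaries are written down, because the nominal windows already have those lengths. This is an inexpensive improvement to a descriptive secondary endpoint and has no bearing on the PK conclusions.

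**What to change.** In SAP 15.1 and 15.1.1:

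- Keep the planned counts and percentages.
- State the start and end of each column. Say explicitly that events after the evening and later evobrutinib doses following the second substrate dose stay in the combination column.
- Add participant-days at risk and TEAEs per participant-day for each column to the overview table.
- Require any statement comparing evobrutinib alone with another column to take these into account. Add a note that the rates are imprecise (about 20 participant-days in each short Part 2 column), assume a roughly constant rate, and do not remove the confounding of treatment with its fixed order.

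The cost is a few sentences in the SAP and a few rows in one table per part. Dose times are recorded under Protocol 6.4 and SAP 9.3 already uses AE start times, so no new data are needed.
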